Blood sample for circulating proteins and metabolite analysis		Cycle 1	Cycle 1	Cycle 1	Cycle 1	Cycle 1				Collect predose and 24h postdose on C1D1. Collect predose and 24 hr post dose on C1D4. Collect predose at all other times. If CRS is suspected, additional blood samples should also be collected if not already scheduled. See Section 8.8.5
Blood sample for TCR sequencing	X	Cycles 1, 2, 3			Cycle 1					Collect predose. See Section 8.8.6
Blood sample for immune cell profiling		Cycle 1, 3	Cycle 1	Cycle 1	Cycle 1	Cycle 1				Collect predose. See Section 8.8.7
Pfizer Prep D1 banked biospecimen(s)		Cycle 1								Collect predose. If not collected on the designated collection day, collect at the next available time point when biospecimens are being collected in conjunction with a participant visit. See Section 8.7.2
Saliva sample for germline comparator		Cycle 1								Collect predose. See Section 8.8.8

Visit Identifier	Screening			atment Per n 28 Day C			EOT Visit	FU Visit	LTFU	Notes/Protocol Section
		Day 1	Day 4	Day 8	Day 15	Day 22				Day 4 Visit is Cycle 1 only
Visit Window	Day -28 to Day -1	Cycles 2 and later ± 3D	-1/+3D	Cycle 1 -1/+3D Cycles 2 and later ± 3D	± 3D	± 3D	≤14D post-final dose	28 to 35 days post-final dose	Q12W ± 14D	
Pharmacokinetics and Immunogenicity Assessments										
Blood sample for PK		Cycles 1-4, 7, 10, etc	Cycle 1	Cycle 1	Cycle 1	Cycle 1	X			Predose, 6 and 24 h postdose on C1D1. Predose and 24 h postdose on C1D4. Predose, 6 h postdose on C1D8; predose only on C1D15, C1D22, C2D1, C3D1, then every 3 rd cycle starting Cycle 4 (ie, C4D1, C7D1, C10D1, etc). If CRS is suspected, additional PK samples should be collected if not already scheduled. See Section 8.5
Blood sample for ADAs and NAbs		Cycles 1-4, 7, 10, etc					X			Predose on C1D1, C2D1, and C3D1 and every 3 rd cycle starting C4 (ie, C4D1, C7D1, C10D1, etc). If AE possibly related to ADA occurs, additional samples for ADA and PK should be collected if not scheduled. See Section 8.9

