a. Dose reduction guidance is not applicable following the first and second doses (priming doses C1D1 and C1D4). If after the C1D4 priming dose, a participant experiences a treatment-related adverse event that leads to dose interruption (ie, dose held on Cycle 1 Day 8), elranatamab treatment may restart at the same dose (32)

Table 2.Dose Modifications for Elranatamab-Related Toxicity and for Peripheral
Sensory or Motor Neuropathy a

mg) upon meeting the redosing criteria (Section 6.6.1). If the 32 mg dose was tolerable, the elranatamab dose should be increased to 76 mg. In case of ongoing CRS or ICANS of any grade on any dosing day, dosing will be held until resolution.

b. Grade 3 or 4 nausea, vomiting or diarrhea must persist at Grade 3 or 4 despite maximal medical therapy to require dose modification or permanent discontinuation.

c. Excludes lymphopenia which is expected based on the elranatamab mechanism of action.

d. For thrombocytopenia: dosing can continue if platelets $\ge 25 \times 109/L$. For Grade 4 (first occurrence), resume at same dose level when platelets $\ge 25 \times 109/L$; for Grade 4 (second occurrence), resumption at a reduced dose level is recommended when platelets $\ge 25 \times 109/L$.

- e. Consider additional diagnostic work-up (see Section 8.3.11)
- f. Excludes laboratory abnormalities that are not considered clinically relevant.

Note: Cycles will not be extended to allow make-up for missed doses.

Doses may be held as needed until toxicity resolution. Appropriate follow-up assessments should be done until adequate recovery occurs as assessed by the investigator.

Missed doses will not be made up and cycles will not be extended to allow for missed doses. A minimum of 2 days should be maintained between the 2 step-up doses (C1D1 and C1D4), a minimum of 3 days between C1D4 dose and the first full dose (C1D8); a minimum of 6 days is required between doses thereafter.

C1D1 will be based on Day 1 of elranatamab dosing. After C1D1, for each cycle, if elranatamab cannot be administered on the planned day (within the window prespecified in the SoA), it should be skipped until the next planned dose (ie, if Day 15 cannot be administered within ± 3 days of planned dose, the dose should be skipped until Day 22).

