## 4. ANALYSIS SETS (POPULATIONS FOR ANALYSIS)

For purposes of analysis, the following analysis sets are defined:

Defined Analysis Set	Description
Safety Analysis Set	The safety analysis set in each cohort will include all enrolled participants in the respective cohort who received at least one dose of study intervention. This will be the primary analysis population for evaluating participant characteristics, treatment administration/compliance and safety endpoints.
Final Analysis Evaluable Set	The final analysis evaluable set in each cohort will include all enrolled participants in the respective cohort who received at least one dose of study intervention. This will be the primary analysis population for evaluating efficacy endpoints. This is the same as the safety analysis set thus only the "safety analysis set" terminology will be used.
Interim Analysis Evaluable Set A	The interim analysis evaluable analysis set A will include the first 90 enrolled participants who received at least one dose of study intervention in Cohort A. This will be the primary analysis population for evaluating efficacy endpoints at the interim analysis for Cohort A.

Interim Analysis Evaluable Set B	The interim analysis evaluable analysis set B will include the first 30 enrolled participants who received at least one dose of study intervention in Cohort B. This will be the primary analysis population for evaluating efficacy endpoints at the interim analysis for Cohort B.
PK Analysis Set	The PK analysis set is a subset of the safety analysis set and will include participants who have at least one postdose concentration measurement.
Immunogenicity Analysis Set	The immunogenicity analysis set is a subset of the safety analysis set and will include participants who have at least one sample tested for ADA.
Biomarker Analysis Set	The biomarker parameter analysis set in each cohort is a subset of the safety analysis set and will include participants who have at least one baseline biomarker assessment.
	Analysis sets will be defined separately for biomarkers based on blood, saliva, and bone marrow samples.
PRO Analysis Set	The PRO analysis set in each cohort will include all participants in the safety analysis set who completed a baseline (last PRO assessment prior to or on the first dose of study intervention) and at least one post-baseline PRO assessment.

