# 6.3. Other Secondary Endpoints

#### 6.3.1. Pharmacokinetic/Pharmacodynamics

Pharmacokinetic analyses will be based on the PK Analysis Set.

A listing of elranatamab concentrations by study visit and timepoint will be generated.

Summary statistics will be provided for pre-dose and post-dose elranatamab concentrations at scheduled visits and nominal timepoints. Values below the limit of quantitation will be treated as zero in the descriptive statistics calculations. For additional details on handling missing and BLQ values, please refer to Section 5.3.1. The summary table will include the number of participants, number of samples with BLQ values, mean, standard deviation, percent coefficient of variation (%CV), median, minimum, maximum, geometric mean, and geometric %CV. For this summary, samples that meet the following conditions will be included:

- For pre-dose samples, have the sample collected before the next dose administration,
- For the 6-hour and 24-hour post-dose samples, have the sample collected within  $\pm$  25% of the nominal scheduled time,
- At least 2 consecutive planned doses were administered without interruption or reduction prior to trough sample collection,
  - Ex. C1D8 predose is included in the summary if C1D1 and C1D4 were administered as planned (ie, 12 and 32 mg, respectively),

• Ex. C1D15 predose is included in the summary if C1D4 and C1D8 were administered as planned (ie, 32 and 76 mg, respectively).

Box and Whiskers plots of elranatamab trough concentrations after multiple doses for participants from the PK Analysis Set who meet the conditions stated above will be presented by study visit. The Box and Whiskers plots will be overlaid with geometric means.

In addition, the PK data from this study may be combined with PK data from other studies to develop a population PK model. The correlation between elranatamab exposure parameters and pharmacodynamic biomarker, efficacy and/or safety outcomes will be explored if data allow. Details of these modeling analyses are not within the scope of this SAP and will be described in a separate population PK and exposure response analysis plan.

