# 6.7.1.1. Adverse Events of Special Interest

Adverse events of special interest (AESI) includes the following events:

- CRS: PT coded as "cytokine release syndrome" and collected on the AE CRF page;
- ICANS: PT coded as "immune effector cell-associated neurotoxicity syndrome" and collected on the AE CRF page;
- Peripheral neuropathy: Standardized MedDRA Queries (SMQ) Peripheral Neuropathy (narrow and broad excluding PTs included in the Guillain-Barre syndrome SMQ) and Guillain-Barre syndrome SMQ (narrow).

CRS and ICANS will be assessed according to ASTCT criteria. All the analyses will be performed for each individual AESI separately.

For CRS and ICANS, the 4 participants who received 44 mg priming dose will be summarized separately within each summary table.

A high-level summary of each AESI will include the number and percent of participants with, separately:

- Any AESI;
- Serious AESI;

- AESI by maximum toxicity grade;
- Had >1 AESI (for CRS and ICANS only);
  - Note: If there are >1 AESI with different grades between two doses, it will be considered as one event;
- Had ICANS concurrent with CRS (for ICANS only). Note: if both CRS and ICANS occurred between the same two doses they will be considered as concurrent;
- AESI leading to dose interruptions;
- AESI leading to dose reductions;
- AESI leading to dose interruptions or reductions;
- AESI leading to permanent discontinuation of study intervention;
- AESI with outcome as resolved.

In addition, the following summary will be provided with descriptive statistics as well as broken down in categories by the time to onset, resolution, and duration of the AESI:

- Time to onset of the AESI;
- Time to resolution of the AESI;
- Duration of each AESI event.

For CRS and ICANS, time relative to dose (ie, after the first dose, after the second dose, after the third dose, after >3 doses) will also be summarized with descriptive statistics.

A summary of AESI symptoms will be provided as follows. The most severe symptom will be summarized if participants have multiple occurrences of AESI symptoms.

- The CRS symptoms (fever, hypoxia and hypotension) as collected on the 'CRS AE' CRFs will be summarized by symptom grade using frequency counts and percentages;
- The ICANS symptoms as collected on the 'ICANS' CRFs will be summarized using frequency counts and percentages;

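### SAP 6.3.1 puts no dose condition on 6 h and 24 h post-dose PK samples, so any valid C1D1 samples from the 4 participants given 44 mg would be pooled with the 12 mg rows

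*SAP*

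**What the plan says.** SAP 6.3.1 sets the structure of the PK table: "Summary statistics will be provided for pre-dose and post-dose elranatamab concentrations at scheduled visits and nominal timepoints". It then lists the conditions a sample must meet to enter the summary.

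- Pre-dose samples must be drawn before the next dose.
- Post-dose samples have a timing condition: "For the 6-hour and 24-hour post-dose samples, have the sample collected within" ±25% of the nominal time.
- The dose condition reads: "At least 2 consecutive planned doses were administered without interruption or reduction prior to trough sample collection". Both examples given are pre-dose samples; one is "Ex. C1D8 predose is included in the summary if C1D1 and C1D4 were administered as planned (ie, 12 and 32 mg, respectively".

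The PK Analysis Set (SAP section 4) "will include participants who have at least one postdose concentration measurement" and has no dose criterion. The Schedule of Activities (Protocol 1.3) asks for PK samples "Predose, 6 and 24 h postdose on C1D1".

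The planned C1D1 dose is 12 mg (Protocol 1.1 and 6.1.1; the planned Cycle 1 total in SAP 6.6.3 also starts from 12 mg). SAP 6.6.3 nevertheless tabulates how many participants received 44 mg at the C1D1 visit, and SAP 6.7.1.1 gives the number and their handling: "For CRS and ICANS, the 4 participants who received 44 mg priming dose will be summarized separately within each summary table".

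**The concern.** The SAP treats a 44 mg priming dose as different enough from 12 mg to need its own line in the CRS and ICANS tables. Its trough rule, by its own example, also drops these participants from the C1D8 pre-dose row. The C1D1 post-dose rows have no matching protection. A correctly timed 6 h or 24 h sample enters the summary whatever dose preceded it.

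A reader would naturally take the C1D1 6 h and 24 h rows as the concentrations that follow a 12 mg dose. If up to 4 values in those rows follow a dose 3.67 times larger, the mean, the spread and above all the maximum no longer describe 12 mg, and nothing in the table would say so.

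**Working it through.** The plan states no figure to reproduce. The check has two parts: whether any provision closes the gap, and how large the effect would be.

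**Does anything else in the SAP separate or remove these samples?**

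- The dose condition in 6.3.1 names trough collection. It cannot be stretched to C1D1 post-dose samples, because two consecutive doses cannot come before a sample taken after the first dose. Applied to those samples it would empty the rows.
- SAP section 4 sets no dose criterion for the PK Analysis Set.
- SAP 5.3.1 sets a concentration to missing if it was not done or not sampled, if the sampling-time deviation is of sufficient concern, or if the clinical pharmacologist flags it as anomalous. None of these is based on dose.
- Protocol 9.4.3.2 also summarises by visit and timepoint only.

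Following the rule as written therefore pools the two doses at C1D1 6 h and 24 h wherever valid samples exist.

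**Size of the effect**

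Inputs from the documents:

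- N = 123 + 64 = 187 treated (Protocol 9.2)
- 4 participants with a 44 mg priming dose (SAP 6.7.1.1), given at C1D1 (SAP 6.6.3)
- planned C1D1 dose 12 mg

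Assumptions not in the documents:

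- concentrations proportional to dose
- all 187 participants contribute a valid sample
- the same within-dose CV in both groups, taken as 50% with a range of 30% to 80%

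Share of 44 mg participants: w = 4/187 = 0.0214. Dose ratio: r = 44/12 = 3.667.

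Arithmetic mean relative to 12 mg alone:
(1 − w) + w·r = 0.9786 + 0.0214 × 3.667 = 1.057, an increase of 5.7%.

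Geometric mean relative to 12 mg alone:
exp(w·ln r) = exp(0.0214 × 1.299) = 1.028, an increase of 2.8%.

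Arithmetic CV, with c the within-dose CV:
√{(1 + c²)[(1 − w) + w·r²] − 1.057²} / 1.057. For c = 0.50 this is √(1.583 − 1.117)/1.057 = 0.645.

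Geometric CV:
√{exp[ln(1 + c²) + w(1 − w)(ln r)²] − 1}. For c = 0.50 this is 0.543.

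| Assumed within-dose CV | Pooled arithmetic CV | Pooled geometric CV |
|---|---|---|
| 30% | 48.5% | 35.9% |
| 50% | 64.5% | 54.3% |
| 80% | 92.7% | 83.6% |

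Median: with 183 participants at 12 mg (187 − 4) it is the 92nd ordered value. With 4 high values added it is the 94th of 187. A shift of two ranks is negligible.

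Maximum: with a 3.67-fold dose the largest value would probably come from a 44 mg participant, though less surely as the within-dose CV rises.

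**The case against.** The best case for leaving the text alone is that this is a descriptive table with no hypothesis attached, and that a reader is not wholly uninformed. Concentrations are also listed by visit and timepoint, SAP 6.6.3 reports how many received 44 mg at C1D1, and the table gives a median and a geometric mean, which are less sensitive than the arithmetic mean. The clinical pharmacologist could set individual values to missing. The table layout is not shown, and 6.3.1 does not forbid a split by dose. All of this is fair and limits the importance of the point. It does not remove it: the anomaly flag is discretionary, a correctly measured concentration after 44 mg is not anomalous, and nothing in the SAP calls for a split.

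A second objection also stands in part. The documents do not show that these 4 participants have C1D1 6 h and 24 h samples. The change history says the two-step priming regimen, with an added visit and sample collections, came in with Amendment 5, and the 4 may have been dosed under an earlier schedule that is not available here. The pooling is therefore conditional on valid samples existing.

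Several stronger readings are tempting but not supported:

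- A reader might infer that the C1D8 6 h row also mixes 76 mg with 32 mg restarts. The dose-modification footnote in Protocol 6.6.2 describes a dose held on C1D8, and nothing shows a 32 mg restart being sampled as C1D8 6 h.
- A reader might infer that the case for the 12 mg step-up dose is affected. The exposure–CRS regression in Protocol 4.3 used Study C1071001 data, and SAP 6.3.1 leaves exposure–response modelling to a separate plan.
- A reader might infer that the PK and CRS tables cover different participants. SAP 6.7.1.1 keeps the 4 within each CRS and ICANS table and summarises them separately there.
- A reader might compute a larger effect for a single cohort. That needs a cohort split of the PK table, which SAP 5.2 and 6.3.1 do not specify, and the cohort of the 4, which is not given.

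**Conclusion.** The point holds as a small gap in SAP 6.3.1. Post-dose samples are admitted on timing alone, so valid C1D1 samples after 44 mg would be summarised with those after 12 mg, in contrast to the SAP's own handling of the same participants for CRS and ICANS.

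The arithmetic mean would be overstated by about 6% and the geometric mean by about 3%. An assumed CV of 50% would appear as about 65%, and the maximum would probably belong to a 44 mg participant. These sizes rest on dose proportionality, an assumed CV, and full sampling of all 187 including the 4. With no valid C1D1 post-dose samples from the 4 there would be no effect. The primary ORR analysis, the interim boundaries and the safety hold rules are untouched.

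**What to change.** Add one sentence to SAP 6.3.1: C1D1 6 h and 24 h concentrations are summarised by the dose actually received at that visit, with participants given 44 mg shown separately from those given 12 mg, in line with 6.7.1.1. For a group this small a listing, or the minimum and maximum, is enough. SAP 5.3.1 already falls back to minimum and maximum when fewer than 3 evaluable values are available.

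The cost is one filter on exposure data already collected. At most 4 of 187 participants leave the 12 mg rows, leaving up to 183. No data are lost, because their values are still reported, and no dosing or clinical rule changes.

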# 6.3.2. Immunogenicity

Immunogenicity data will be analyzed in the Immunogenicity Analysis Set. The percentage of participants with positive ADA will be summarized. Listings and summary tabulations of the ADA data at baseline and post-baseline will be generated. Samples may also be analyzed for the presence of neutralizing antibodies (NAb), and any data will be similarly summarized. For participants with positive ADA or NAb, the magnitude (titer), time of onset, and duration of ADA or NAb response will also be described, if data permit.

The potential impact of immunogenicity on PK and clinical response including pharmacodynamic markers, safety/tolerability and efficacy will be explored, if warranted by the data. This analysis may be reported separately from the CSR.

# 6.4. Exploratory Endpoints

The following exploratory endpoint analyses may be performed. The non-efficacy results may be presented separately from the main CSR.

# 6.4.1. Efficacy Analysis

# 6.4.1.1. Sustained MRD Negativity Rate

Sustained xx-month MRD negativity rate is defined as the proportion of participants with negative MRD per IMWG sequencing criteria and confirmed sCR/CR with at least xx months apart without positive MRD in between, from the date of first dose until confirmed PD, death or start of new anticancer therapy, whichever occurs first, where xx = 6, 12 and 24 months. Sustained xx-month MRD negativity rate will be calculated along with the 2-sided 95% CI using the Clopper-Pearson method.

# 6.4.1.2. Duration of MRD Negativity

If data permits, DOMRD negativity will be analyzed using Kaplan-Meier method in participants who have achieved negative MRD per IMWG sequencing criteria and confirmed sCR/CR. DOMRD is defined, for participants with negative MRD, as the time from first documentation of negative MRD to the date of first documentation of relapse or death due to any cause, whichever occurs first. Relapse is defined as any one or more of the following criteria:

- Loss of MRD negative state (evidence of clonal plasma cells on NGS, or positive imaging study for recurrence of myeloma);
- Reappearance of serum or urine M-protein by immunofixation or electrophoresis;
- Development of  $\geq$ 5% clonal plasma cells in the bone marrow;
- Appearance of any other sign of progression.

DOMRD negativity will be censored on the date of the last adequate disease assessment for participants who do not have an event (relapse or death), on the date of the last adequate disease assessment before the new anticancer therapy for participants who start a new anticancer therapy prior to an event, or on the date of the last adequate disease assessment before the 2 or more missing disease assessments for participants with an event after 2 or more missing disease assessments.

#### 6.4.2. Biochemical Response Rate

Biochemical BOR will be reassessed programmatically based on derived responses per IMWG from the date of first dose until confirmed disease progression using IMWG response criteria, death or start of new anticancer therapy, whichever occurs first. This exploratory analysis will follow the same rules as the primary analysis except for deriving response based on the local laboratory and bone marrow data and excluding the individual lesion data provided by BICR or investigator.

#### 6.4.3. Biomarker Analysis

Biomarker data including DNA, RNA, protein, metabolites, or defined cell types resulting from analyses of peripheral blood, saliva and/or BM biospecimens will be assessed based on the Biomarker Set.

Exploratory biomarker endpoints will not be reported in CSR, but in a separate biomarker report.

#### 6.4.4. Patient-Reported Outcomes

The following PRO analyses will be performed to support the CSR development. All other PRO analyses described in the study protocol but are not included in this SAP will be described in detail in a separate PRO analysis plan. Analysis of the PRO endpoints except the PRO completion table will be based on the PRO Analysis Set.

All PRO analyses will be carried out for each cohort separately. The PRO analyses will be based on the instruments EORTC QLQ-C30, EORTC QLQ-MY20, EORTC QLQ-CIPN20, EQ-5D index, EQ-5D VAS, and PGIS/ PGIC.

# **Completion Status**

For each cohort at each time point, the number and percentage of participants who completed these instruments will be summarized, as will the reasons for non-completion of these measures. An instrument is considered completed if at least one item was answered by the participant.

# EORTC QLQ-C30

This questionnaire contains 30 questions organized into 5 multi-item functional scales, 3 multi-item symptom scales, a global health/quality of life scale, and 6 single item symptom scales. For each of the 15 scales, the results will be summarized using descriptive statistics including mean, standard deviation, 95% CI, median, minimum, maximum at each timepoint. This will be done based on the observed values as well as change from baseline values.

